7.3 RANDOMIZATION

Women who have met all inclusion criteria and have none of the exclusion criteria, and who have signed the informed consent, will be scheduled for a randomization visit. Prior to the randomization visit all women who did not have a blood collection at the screening visit will be advised to fast for at least twelve hours prior to the visit. A blood sample will be collected for central analysis and a local sample for assessment of INR if needed. Data to be collected are indicated in Table 2.

Randomization to one of the four possible study groups (active HRT and placebo antioxidants, active HRT and active antioxidants, placebo HRT and active antioxidants, placebo HRT and placebo antioxidants) will be by a telephone call to the Study Coordinating Center. After confirmation of the patient's eligibility the SCC will issue a

unique patient identifier and medication codes that the clinical center coordinator will use to obtain the woman's study medications. The unique patient identifier will be used on all study forms, laboratory samples, angiograms and any other necessary study documents. Each woman will have a one in four chance of being assigned to each of the four study groups. Randomization will be stratified by clinical center (n=5) and by whether a hysterectomy has been performed. Each woman will be given a seven month supply of her study medications, a medication instruction sheet, a bleeding calendar for those women with a uterus, a bottle of Centrum Silver vitamins (if she requests it), and an appointment for the one month visit.

TABLE 2

WAVE Summary	Screening	Randomization	IM	3M	6M	12M	18M	24M	30M	36M	Exit
Consent	X										
Creat, trig, FSH (if needed)	X										
INR	Obtain at either visit		X								
Study Bloods	Obtain at either visit			X			X			X	
Ht/wt, BP, waist/hip	Obtain at either visit					X		X		X	
Randomization form		X									
Breast, pelvic, Pap, mamm, breast self-exam teaching	X					X		X		X	
Sign medical release	X					X		X		X	
Brachial reactivity	Obtain between consent and initiation of study medication			X							
Dipyridamole SPECT/ETT				X						X	
ECG		X				X				X	
Patient tracking form		X			Update as needed						
Bleeding calendar		X	X	X	X	prn	prn				
Dispense study meds		X			X	X	X	X	X		
Adherence assessment					X	X	X	X	X	X	X
Quality of Life		X		X			X		X		
Follow-up visit*					X	X	X	X	X	X	X
Angiogram	X										X
Physical exam		X				X		X		X	

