10.2.2 Primary Analysis

The change in MLD will be computed for each of the patient's study endpoint segments . The follow up angiogram is not necessarily the same for all the segments in a patient: for segments that were revascularized prior to the concluding angiogram, the MLD will be read from the angiogram before the revascularization. For segments that were not revascularized before the concluding angiogram, the MLD will be read from the concluding angiogram. Each of the changes in MLD will then be divided by the time between the entry angiogram and the follow up angiogram. For patients who have revascularization procedures prior to the concluding angiogram, the changes in MLD of various segments may thus be divided by different quantities. These changes in MLD, divided by the appropriate quantities are then averaged for the patient. This average is the primary endpoint for the patient. A segment with a 1 mm change at the time of an intercurrent angiogram at 6 months will therefore have more weight in the average than another segment with a 1 mm change after 3 years. With the time adjustment described above, the primary endpoint is basically a measure of the average rate of change in MLD in diseased segments.

The primary endpoint in the treated and control groups will be compared using a nonparametric rank test based on the Van der Waerden scores. This test, which is similar to a Wilcoxon test, was selected for two reasons. First, for the sample sizes contemplated in this study, it has essentially the same power as the usual t-test under the assumption of normality and

better power than the t-test if the data are markedly non-normal. Second, it readily accommodates patients who had an MI or died by assigning them the worst rank. It also has better power than the Wilcoxon test under the assumption of normality. The primary analysis for the study will be conducted using the “intention to treat” paradigm, with all patients retained in their original randomization group, regardless of their level of compliance with their assigned treatments.

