10.4 SAMPLE SIZE CALCULATIONS

The sample size calculations are based on a change in mean MLD using a t-test. The antioxidant and HRT components are treated as separate trials (no interaction is assumed). No adjustment for multiple comparisons will be made.

The type 1 error rate α was 0.05 (2-tailed). Although a rank test will be used, given the sample sizes contemplated in the study, the power of the rank test is essentially the same as that of the t-test under the assumption of normality. The power calculations are based on the effect size, defined as the expected difference in outcome between treatment and control divided by the

standard deviation of the outcome (the outcome here is the change in mean MLD between baseline and follow-up). The effect sizes for four published studies are summarized below.

STARS	FATS	SCRIP	MARS
0.86	0.51	0.29	0.14

The weighted average of these effect sizes, weighing by the number of patients in each study is 0.334. With this effect size and a power of 0.90, the required total sample size is N=380. Assuming a dropout rate of 15%, 450 patients are needed. If a 20% dropout rate is assumed, the power of the test for various effect sizes is summarized in the table below:

	N=450	N=425	N=400	N=375	N=350
ES=0.30	0.81	0.79	0.77	0.74	0.71
ES=0.35	0.91	0.90	0.88	0.86	0.83
ES=0.40	0.97	0.96	0.95	0.93	0.92

Based on these considerations, 400 patients is considered the minimum acceptable sample size for the study. The target sample size for the study is 450 patients.

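### The primary rank test is specified without the randomization strata, the other factorial treatment or baseline MLD: valid, but it forgoes a small, nearly free gain in precision

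*Protocol*

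**What the plan says.** On the test, protocol section 10.2.2 says: "The primary endpoint in the treated and control groups will be compared using a nonparametric rank test based on the Van der Waerden scores". It gives two reasons. One is power: close to the t-test under normality, better when the data are clearly non-normal, and better than the Wilcoxon test under normality. The other concerns clinical events: "Second, it readily accommodates patients who had an MI or died by assigning them the worst rank". Adjustment is not discussed.

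On the endpoint, each segment's change in MLD is divided by its own follow-up time, and "These changes in MLD, divided by the appropriate quantities are then averaged for the patient". Baseline therefore enters by subtraction only.

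On the design, section 7.3 says: "Randomization will be stratified by clinical center (n=5) and by whether a hysterectomy has been performed". It also says: "Each woman will have a one in four chance of being assigned to each of the four study groups". Section 10.4 treats the hormone and antioxidant comparisons as two separate trials without interaction, and adds: "The sample size calculations are based on a change in mean MLD using a t-test".

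On baseline readings, section 12.2.9 has the central laboratory review entry films semiquantitatively within a week, for quality and eligibility. It plans automated quantitative analysis of all baseline and follow-up films once the follow-up examination is complete.

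For the angiographic outcomes, multivariate or covariate analysis is mentioned only for the by-segment analyses (10.3.2) and the post-PTCA restenosis analysis (10.3.3).

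**The concern.** The protocol chose its primary test partly for power. It then leaves out of that test information it will hold anyway: ten randomization strata (five centers by hysterectomy), the assignment to the other treatment, and the baseline measurement.

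If any of these predicts the endpoint, the variation it explains stays in the error term. Balancing on strata and then ignoring them makes the test slightly conservative when the strata are prognostic. If the other treatment works, as the trial hopes, its effect adds spread to both arms of each comparison. Subtracting baseline MLD is not the same as adjusting for it, because the change may still depend on where a lesion started.

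At stake is precision only. Allocation is balanced on both factors, so leaving these terms out creates no bias.

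**Working it through.** **Inputs from section 10.4:** effect size 0.334 (difference divided by SD), two-sided alpha 0.05, power 0.90, 380 evaluable women, 15% dropout, 450 randomized.

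**Step 1. The plan's own figure.** For an unadjusted comparison of two means:

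- n per arm = 2 × (1.960 + 1.282)² / 0.334² = 188.4, so 189 per arm and 378 in total (stated 380).
- 380 / 0.85 = 447.1, so 448 (stated 450).
- All 15 cells of the 20%-dropout power table reproduce within one point.

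The stated power therefore does not depend on adjustment.

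**Step 2. Power if covariates explain a share R² of the variance.** The residual SD becomes √(1 − R²). With 380 evaluable women, power ≈ Φ(0.334 × √(380/4) / √(1 − R²) − 1.960):

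- R² = 0: Φ(3.255 − 1.960) = 0.902
- R² = 0.05: Φ(3.340 − 1.960) = 0.916
- R² = 0.10: Φ(3.432 − 1.960) = 0.929

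The t-distribution gives 0.901, 0.915 and 0.928. The total needed for 90% power is 378, 358 and 340, a saving of 20 or 38 evaluable women. The documents give no R², so 0.05 and 0.10 are assumptions.

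**Step 3. The other treatment alone.** If it also has effect size 0.334 and is allocated 1:1, it adds (0.334/2)² = 0.028 to a within-group variance of 1, an R² of 0.028/1.028 = 0.027.

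**Step 4. Simulation.** 380 women, ten strata, 4,000 runs per case (Monte Carlo standard error about 0.5 point). The plain Van der Waerden test is compared with a linear model on the same normal scores. The other treatment has effect size 0.334 and the stratum SD is 0.15 (both assumed), except in the row with nothing prognostic.

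| Case | Plain test | + strata and other treatment | + baseline covariate |
|---|---|---|---|
| Nothing prognostic | 0.908 | 0.910 | 0.907 |
| Strata and other treatment only | 0.890 | 0.900 | 0.900 |
| Baseline coefficient 0.05 | 0.895 | 0.900 | 0.918 |
| Baseline coefficient 0.10 | 0.888 | 0.895 | 0.920 |
| No treatment effect, baseline coefficient 0.10 | 0.050 | 0.054 | 0.051 |

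The baseline coefficient is the share of variance explained by baseline before strata and treatment effects are added.

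Strata and the other treatment gain about 1 point. Baseline adds roughly 2 more at the assumed shares. When nothing is prognostic, adjustment costs nothing visible. Type I error stays near 5% throughout.

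**Step 5. Worst ranks.** With a random 10% of women given the worst rank (assumed, unrelated to treatment) and a baseline coefficient of 0.10, power is 0.693, 0.704 and 0.728 in the same column order, with type I error 0.055, 0.057 and 0.056. The lower level comes from the worst-rank rule, a separate matter. The ordering of the three analyses is unchanged.

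**The case against.** The strongest reply is that section 10.2.2 never calls the test unstratified or unadjusted. Van der Waerden scores can be used in a stratified test, and such terms are often left to a statistical analysis plan, which is not shown here. This stands in part: if that plan adds the terms, the point is met. But the section names and defends a two-group comparison, and a reader who follows it as written runs one without strata or covariates.

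Four stronger readings are tempting, and the documents do not support them:

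- *The plain test is wrong or the trial underpowered.* A reader might infer that power is already tight. The stated 90% reproduces without adjustment, and type I error is about 5%.
- *The strata are known to be prognostic.* The protocol does not say that center or hysterectomy predicts change in MLD. Hysterectomy determines which hormone preparation a woman receives (section 4.1), which is a different matter. Whether to show the hormone effect by hysterectomy is a subgroup question and no part of a precision argument.
- *The gain from baseline follows from the textbook ratio (1 + r)/2.* That ratio is for a simple change score with equal variances. This endpoint averages segment changes over differing times, includes lesions new at follow-up, sets near-total occlusions to zero and is then ranked with events at the bottom. The ratio does not transfer.
- *Baseline MLD is already in hand at entry.* Section 12.2.9 says otherwise: the entry review is semiquantitative and the quantitative reading comes later. For a woman who dies before follow-up angiography, the timing of that reading is not stated. This objection stands and shapes the fix, because such women are kept through the worst rank and must not be lost for want of a covariate.

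**Conclusion.** The point holds as an efficiency improvement. Section 10.2.2 fixes a valid primary test that reaches its planned power but does not use the trial's own strata, the other assignment or baseline MLD as a covariate. The expected gain is small to moderate: about 1 power point from strata and the other treatment, and a rise from 0.90 to about 0.915 to 0.928 at 380 women and effect size 0.334 if all covariates together explain 5% to 10% of the variance. These sizes rest on the assumed R², stratum SD and effect of the other treatment, none of which the protocol gives. That the change is nearly free does not rest on them: both reasons given for the rank test survive adjustment, and the simulation showed no visible loss when nothing was prognostic.

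**What to change.** In section 10.2.2:

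1. Keep the Van der Waerden scores and the worst-rank rule for MI and death. Make the primary test of each factor a regression of the scores on treatment, center, hysterectomy, the other factor's assignment and baseline MLD. A stratified form of the rank test is an alternative for the strata.
2. Define the baseline covariate as the mean entry MLD of segments with 15-75% stenosis at entry. Lesions first seen at follow-up are endpoint segments too (section 10.2.1), but they are identified after randomization and must not define the covariate.
3. State in section 12.2.9 that baseline films are also read quantitatively for women who die or have no exit angiogram, so that no woman with an assigned rank leaves the analysis because her covariate is missing.
4. Keep the unadjusted two-group test as a sensitivity analysis.

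The cost is a few lines of wording, fixed before unmasking so that the covariates cannot look chosen after the fact. The one possible extra task is the quantitative reading of baseline films for women without a follow-up film. Section 12.2.9 already plans quantitative analysis of all baseline angiograms, so this mainly settles when those films are read.

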10.3 Secondary Analyses

10.3.1 By Patient Analyses

- a) *By patient, change in the mean (rather than minimum) lesion diameter of all study endpoint segments.* The mean segment diameter extends over a segment length that is identical on the entry and exit angiogram.

- b) *By patient, change in the mean diameter of non-disease containing segments (i.e. segments that do not contain a lesion $\geq 15\%$ on either the entry or exit angiogram).* The mean segment diameter extends over a segment length that is identical on the entry and exit angiogram. Segments included in this analysis must be in the main coronary vessels or their major branches and at least 1.5 mm in diameter.

- c) *By patient, analysis based on categorizing patients as exhibiting overall progression, regression, mixed change or no change.* To classify patients, the MLD of each study endpoint segment will be categorized as decreasing by > 0.4 mm (progression), increasing (regression) by > 0.4 mm or neither (no change). A patient will be categorized as exhibiting
 - overall progression if they have at least one segment progression without any segment regression,
 - overall regression if they have at least one segment regression without any segment progression,
 - mixed change if they have both progressing and regression segments, and
 - no change if none of their segments have progressed or regressed.

The analysis will be repeated using the mean (instead of the minimum) lesion diameter of study endpoint segments, and then for the mean lumen diameter of non-diseased segments

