10.2 PRIMARY ENDPOINT

10.2.1 Definition of the Primary Endpoint

The primary endpoint will be evaluated in all segments containing 15 - 75% lesions noted on the entry angiogram or any new lesions \geq 15% observed on a follow-up angiogram

within the study duration. These segments are referred to as the study endpoint segments. The change in MLD of each segment is divided by the time between the entry arteriogram and the final angiogram within the prespecified study follow-up-period. An exception will be made for intercurrent angiograms and revascularization procedures: these procedures will provide the concluding measurements for those segments that were intervened. For such segments, the change in MLD will be divided by the time between the baseline angiogram and the pre-procedure intercurrent angiogram. The study goal is to obtain a protocol angiogram within the last six months of the scheduled end of the trial. With recruitment anticipated to occur over a 12-15 month period, this implies an anticipated average follow-up of approximately 40.5 months. If the patient has had a coronary angiogram for clinical indications within six months of the planned study termination, the results from that arteriogram can be used in lieu of an exit angiogram. If the angiogram has occurred more than six months before the end of the trial an additional angiogram will be requested.

Patients eligible for entry into the study will have one or more segments containing 15 - 75% stenosis which have not been influenced by prior catheter interventions. These are referred to as qualifying segments and lesions. Segments identified on the entry as containing a 15 - 75% stenosis or on the concluding arteriogram(s) as containing any lesion $\geq 15\%$ are considered endpoint segments. This definition automatically includes those segments which originally qualified the patient for study entry. Segments included in this analysis must be in the main coronary vessels or their major branches and have a reference diameter >1.5 mm. Segments or lesions progressing to 99 - 100% stenosis are automatically assigned a MLD of 0.0 mm. Non-visualized segments distal to total occlusions are considered lost to follow-up.

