10.3.2 By Segment Analyses

(This provides the opportunity to include lesion, segment and vessel characteristics unique to each lesion and segment in multivariate analyses).

- a) *By segment, change in MLD of all study endpoint segments.* The change is adjusted for the actual time interval between the entry arteriogram and the follow-up arteriogram(s).
- b) *By segment, change in the mean (rather than minimum) lesion diameter of all endpoint segments.* The mean segment diameter extends over a segment length that is identical on the entry and exit angiogram.
- c) *By segment, change in the mean diameters of all non-disease containing segments (no lesion \geq 15% on either the entry or exit angiogram).* The mean segment diameter extends over a segment length that is identical on the entry and concluding angiogram. Segments included in this analysis must be in the main coronary vessels or their major branches and at least 1.5 mm in diameter.
- d) *By segment, change in the mean diameters of quantitated segments.* This includes both study endpoint segments and quantitated segments with no lesion \geq 15%. The segments included in this analysis must be in the main coronary vessels or their major branches, and must be at least 1.5 mm in diameter. The mean segment diameter extends over a segment length that is identical on the entry and concluding angiogram.

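### The non-diseased-segment secondary analyses select segments on the exit film as well as the entry film, so the arms are compared on sets shaped by progression after randomization

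*Protocol*

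**What the plan says.** Section 10.3.1(b) defines the by-patient analysis as "change in the mean diameter of non-disease containing segments (i.e. segments that do not contain a lesion" of at least 15% on either the entry or the exit angiogram. Section 10.3.2(c) applies the same rule by segment: "change in the mean diameters of all non-disease containing segments (no lesion" of at least 15% on either film).

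Section 10.3.1(c) classifies patients as progressing, regressing, mixed or unchanged. Its main version uses endpoint segments: "the MLD of each study endpoint segment will be categorized as decreasing by > 0.4 mm (progression"). It is repeated for the mean diameter of those segments, "and then for the mean lumen diameter of non-diseased segments". Only this last repeat uses the non-diseased set.

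Segments that acquire a lesion go elsewhere. Section 10.2.1 counts "any new lesions \geq 15% observed on a follow-up angiogram" among the study endpoint segments. Section 10.3.2(d) pools everything quantitated: "This includes both study endpoint segments and quantitated segments with no lesion \geq 15"%. It is a by-segment analysis only.

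**The concern.** The exit film is the outcome measurement, and here it also decides which segments are analyzed. Take a segment that is clean at entry and would narrow to 15% or more without treatment. In the control arm it narrows and is dropped, along with its loss of diameter. If treatment prevents the narrowing, the matching segment in the active arm stays in with its smaller loss. The two arms then contribute differently selected segments, and the selection is by the process under study.

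What is at stake is the reading of 10.3.1(b), the protocol's by-patient measure of change in vessel without lesions. No by-patient analysis follows all segments that were clean at entry. In 10.3.1(a) the new lesions are averaged with lesions already present at entry, and 10.3.2(d) is pooled in the same way and is not by patient.

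**Working it through.** **The plan's own figures.** The protocol gives no sample size or expected effect for the non-diseased-segment analyses. Its only calculation (section 10.4) is for the primary endpoint: effect size 0.334, power 0.90, two-sided 0.05. Per arm, 2 × (1.960 + 1.282)² / 0.334² ≈ 188.4, so 189 per arm and 378 in total, against 380 stated. For 15% dropout, 380 / 0.85 = 447.1, so 448, against 450 stated. These reproduce, and the present point does not alter them.

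**Which analyses the rule reaches.**

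| Analysis | Does a new lesion at exit remove the segment? |
|---|---|
| Primary endpoint (10.2), 10.3.1(a) | No, it enters as an endpoint segment |
| 10.3.1(c), main version and first repeat | No, endpoint segments are used |
| 10.3.2(a), (b), (d) | No |
| 10.3.1(b), last repeat of 10.3.1(c), 10.3.2(c) | Yes |

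**Size of the distortion in mean change.** Consider segments that are clean at entry.

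- D is the change in mean diameter, in SD units. F is a standard normal score for focal narrowing.
- ρ is the correlation between diameter loss and F.
- A segment is dropped when F exceeds c, where c is set by the control new-lesion rate p: c = Φ⁻¹(1 − p).
- Treatment raises D by d and lowers F by g.

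Among retained segments the mean of D is raised by ρ·λ(c) in the control arm and by ρ·λ(c + g) in the treated arm, where λ(x) = φ(x)/Φ(x). Hence:

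observed difference = d + ρ·[λ(c + g) − λ(c)].

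Inputs: d = g = 0.334, borrowed from section 10.4 as an illustration. The values of p and ρ are assumptions, because the protocol gives neither.

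| p (control) | λ(c) | λ(c + g) | Bracket | Observed, ρ = 0.3 | Observed, ρ = 1.0 | Attenuation |
|---|---|---|---|---|---|---|
| 5% | 0.1086 | 0.0577 | −0.0509 | 0.319 | 0.283 | 4.6% to 15% |
| 10% | 0.1950 | 0.1142 | −0.0808 | 0.310 | 0.253 | 7% to 24% |
| 20% | 0.3500 | 0.2271 | −0.1228 | 0.297 | 0.211 | 11% to 37% |
| 30% | 0.4967 | 0.3430 | −0.1537 | 0.288 | 0.180 | 14% to 46% |

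For example, at p = 30% and ρ = 1: 0.334 − 0.1537 = 0.180, and 0.1537 / 0.334 = 46%. Simulation with 2 million segments per arm agrees to within 0.001.

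**Boundary cases from the same formula.**

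- ρ = 0: the second term vanishes and the difference stays 0.334.
- g = 0 (no effect on new lesions): the bracket is zero and the difference stays 0.334.
- d = 0, g = 0.334 (focal lesions prevented, mean diameter unaffected): the difference is ρ times the bracket. It runs from 0 to −0.154 SD over the values above, which wrongly favors control.
- d = g = 0: the difference is zero, so a treatment that does nothing gains no false-positive rate from the rule.

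**A check in millimeters.** Assume entry stenosis uniform on 0–15%, focal progression with mean 3 and SD 8 percentage points, and mean-diameter loss of 0.06 mm with SD 0.20 mm. Let treatment cut focal progression by 3 points. About 31% of control and 21% of treated segments drop out. A true 0.060 mm benefit is measured as 0.052 mm at correlation 0.3 and 0.047 mm at 0.5. This represents one high removal rate only.

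Both calculations are at segment level. Patient averages weight segments differently, and no size was computed for the categorical repeat in 10.3.1(c).

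**The case against.** The strongest reply is that the split looks deliberate. Endpoint segments carry focal disease, while segments clean on both films show change where no lesion formed. That second quantity is coherent as a description, and an entry-only set would contain segments that have a lesion at exit. This stands as a reason to keep the both-films set. It does not make that set a sound basis for comparing randomized arms. Section 10.3.3(a) already selects its lesions above 75% on the entry film alone, so an entry-based rule is not foreign to the protocol.

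Three stronger readings are tempting, and the protocol does not support them.

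- A reader might infer that progressing segments vanish from the trial's measure of progression. They do not: sections 10.2.1 and 10.2.2 put them in the primary endpoint, and they also count in 10.3.1(a), most of 10.3.1(c), and 10.3.2(a), (b) and (d).
- A reader might infer that the treatment effect is necessarily understated. Attenuation is the expected direction when treatment affects both kinds of narrowing and they are correlated. Otherwise the bias can be nil, or can favor control.
- A reader might infer that a real effect on early disease would be reported as absent. Even at the extreme of the table about half the effect remains (0.180 of 0.334), and new lesions still contribute to the primary endpoint.

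It is also fair that every magnitude rests on assumed inputs, and that the control new-lesion rate largely drives the result.

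**Conclusion.** The point holds for three secondary analyses: 10.3.1(b), the last repeat of 10.3.1(c), and 10.3.2(c). Their segment sets depend on a post-randomization result that is itself progression, so the between-arm comparison is not protected by randomization. Where treatment affects new-lesion formation and the two kinds of narrowing are correlated, a true 0.334 SD benefit is attenuated by roughly 4.6% to 46% over the assumed ranges. The protocol supplies neither the new-lesion rate nor the correlation, so this shows what is possible and is not an estimate for this trial. The exclusion does not affect the primary endpoint, the sample size, or the type I error when treatment has no effect. Severity is minor to moderate.

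**What to change.** For the between-arm comparison in these three analyses, define the set from the entry film only: no lesion of 15% or more at entry, in a main vessel or major branch, 1.5 mm or larger. Keep each such segment whatever the exit film shows. For segments that are intervened on, take the last measurement from the pre-procedure film, as section 10.2.2 does for the primary endpoint. Report the present both-films set alongside, labeled as a supportive description of change where no lesion formed.

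The cost is protocol wording. Section 12.2.9 already has the central laboratory analyze all baseline and follow-up angiograms quantitatively, so no new films or patients are needed. The drawback is overlap: segments with new lesions will appear both here and in the endpoint-segment analyses, and the entry-defined set will mix focal and diffuse change. Reporting both sets lets the reader see the difference.
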